Title of Study: Modulation of Spontaneous Cortical Activity by tDCS: BRAIN Initiative I

NCT Number: NCT03672747

Date: 04/21/2023

Study Protocol

Transcranial direct-current stimulation (tDCS) is a form of noninvasive brain stimulation that uses small metal electrodes placed on the scalp to deliver a constant, low-amplitude current to brain areas of interest. This current is thought to increase or decrease local neuronal excitability, depending on the brain area and type of stimulation. Anodal stimulation is generally thought to cause neuronal resting-membrane depolarization and decreased local GABA, which in turn increases neuronal excitability and promotes neuronal firing. Cathodal stimulation, on the other hand, is generally thought to cause resting-membrane hyperpolarization and decreased local glutamate, which decreases neuronal excitability and suppresses neural firing. However, these effects have generally been studied in only model systems and the neural effects in the human neocortex are poorly understood. The current study aims to address this gap in knowledge by combining tDCS with a new dynamic neuroimaging method known as magnetoencephalography (MEG). MEG is noninvasive and provides highly accurate measures of ongoing neurophysiology. These measures include spontaneous neural activity, which reflects the background rate of neuronal firing in the absence of endogenous and exogenous input (i.e., the seemingly random discharges that human cortical neurons exhibit), as well as oscillatory activity which reflects information processing among large groups of neurons. Typically, both spontaneous and oscillatory neural activity is divided into frequency bands of activity (e.g., alpha, gamma) and these different bands are thought to roughly correspond to different circuits and/or different cognitive processes. Thus, in this study investigators will evaluate the impact of different types of tDCS on behavior and spontaneous and oscillatory neural activity in healthy adults. Investigators will use a cross-over design where all participants complete all stimulation conditions (i.e., anodal, cathodal, and sham) and will focus on behavioral performance, in terms of accuracy and reaction time, and alpha and gamma frequency neural activity because these two bands have been shown to be critical to visual processing.

Each participant will complete a total of four visits, with each visit being separated by at least one week. The effects of tDCS are thought to last only a few hours so the one-week wash-out period should be more than adequate. During Visit 1, participants will complete cognitive and psychiatric screens and a structural MRI session. This high-resolution structural MRI is needed for tDCS electrode placement using our navigational system and for current flow modeling to derive the optimal placement of electrodes for maximum stimulation of targets. Prior to Visit 2, each participant will be randomized to the sham, anode, or cathode-first group, which will determine the stimulation montage for each of their subsequent visits. Note that all participants will complete each condition (anode, cathode, and sham) during a separate visit. During Visits 2-4, each participant will undergo 20 minutes of high-definition tDCS during a passive visual stimulation paradigm, and then be moved to the MEG chamber for neural recording. During each MEG session, participants will complete measures of perceptual processing. The outcome measures include behavioral changes (i.e., reaction time and accuracy) and neuronal changes (i.e., spontaneous alpha and gamma activity, oscillatory alpha and gamma activity) induced by the different types of stimulation relative to sham.

Statistical Design & Power

Sample Size Considerations: Included are estimates of attrition, MEG success rates based on our prior imaging experiences, and measures of effect size based on the results of our preliminary studies in calculating our necessary sample size. To estimate the effect size, investigators computed Cohen's d using data from a perceptual processing task where participants were assigned to a single stimulation type. Investigators focused on the average effect size for stimulation group differences, which was $d = 0.96$. This suggests that 34 participants per group (anode, cathode, sham) would be adequate to detect differences at 0.01 alpha with 0.90 power. Note that the design of the current study is a cross-over type where each participant will complete all three stimulation conditions in a random order. All things being equal, it would be expected that the effect sizes to be larger in the proposed studies due to the within-subjects design (i.e., the preliminary data used to calculate effect sizes followed a between-subjects design). However, this is not necessarily the case and investigators should be powered to examine sex differences in the impact of tDCS on spontaneous and oscillatory neural activity in future work. Thus, the aim is 124 complete data sets, but it is anticipated that enrollment up to 150 participants to reach this number may be needed, as the multiple visits could lead to larger attrition than we have observed in our pilot studies, and MEG technical difficulties on 3-5% of participants are expected.

Primary Statistical Analyses: The behavioral data analyses will involve computing the accuracy rate for each participant (i.e., the percentage of trials where the participant responded correctly) and the mean reaction time. The reaction time reflects how quickly the participant responded to the visual stimuli presented during the MEG and will be the average of all correct trials during the perceptual processing task, which consists of 240 total

trials. Once these metrics are computed per person, investigators will compute mean accuracy and reaction time for each stimulation condition, which will be the outcome metrics. Faster reaction times and higher accuracy reflect more favorable outcomes following the particular type of stimulation relative to sham and can be assessed using an ANOVA per measure with follow-up post-hoc testing to identify the specific direction of any significant effects. As per the MEG, the raw data will be transformed into the time-frequency domain and imaged, per participant, frequency band (alpha, gamma), and condition, using an advanced beamforming approach. The resulting images are comprised of neural response amplitude values in each of thousands of voxels (i.e., cubes of tissue). Investigators will then compare the amplitude of each voxel for stimulation effects using a whole-brain mass univariate approach in the Statistical Parametric Mapping (SPM12) software. The resulting statistical F-maps of neural oscillatory activity will reveal brain areas with significant differences by stimulation condition, and then use post-hoc testing will be used to derive the direction of the effect. In addition, investigators will extract the time series from these significant clusters by computing a virtual sensor at the peak voxel. These time series will enable us to compute the spontaneous activity level during the baseline period and this will be used to determine whether there are differences in spontaneous neural activity by stimulation condition. For these analyses, separate ANOVAs will be computed for each cluster. Note that all statistical analyses will be done separately for the alpha and gamma maps and multiple comparisons correction will use the Bonferroni method.

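### The stimulation orders are not listed or stated to be balanced over visits, and no analysis includes a visit term, so practice across three sessions can enter the condition contrasts

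*Combined protocol and SAP*

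**What the plan says.** The Study Protocol section describes a cross-over with stimulation at Visits 2, 3 and 4. On allocation it says that "each participant will be randomized to the sham, anode, or cathode-first group, which will determine the stimulation montage for each of their subsequent visits", and adds that "all participants will complete each condition (anode, cathode, and sham) during a separate visit". Sample Size Considerations says that "each participant will complete all three stimulation conditions in a random order". Neither section lists the orders, says how the second and third conditions are set within a group, or says that each condition falls equally often at each visit.

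The stated protection between sessions is time: "The effects of tDCS are thought to last only a few hours so the one-week wash-out period should be more than adequate". Visits are at least one week apart.

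Under Primary Statistical Analyses, reaction time and accuracy "can be assessed using an ANOVA per measure with follow-up post-hoc testing to identify the specific direction of any significant effects". For the MEG images the investigators will "compare the amplitude of each voxel for stimulation effects using a whole-brain mass univariate approach", and for spontaneous activity "separate ANOVAs will be computed for each cluster". All three compare stimulation conditions. None names visit or sequence.

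**The concern.** Each participant does the same 240-trial perceptual task at three sessions. Reaction time and accuracy may well change with practice, whatever the stimulation. The contrasts of interest are anodal and cathodal against sham. If one condition sits later in the visit schedule on average than another, its contrast contains part of the practice effect, and a model with condition alone cannot tell the two apart. A washout does not help, because it does not alter which condition comes at which visit.

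There are two protections: orders that balance visit position, and a visit term in the model. The documents state neither. Whether the contrasts are biased therefore depends on an order list that the reader cannot see.

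**Working it through.** **The plan's own figure.** Sample Size Considerations gives 34 per group for d = 0.96, alpha 0.01 and power 0.90. A two-sided two-sample t-test gives 33.99, so 34 (power 0.9001). The figure is reproduced and does not depend on order. The plan gives no figure for the orders, so the rest is a design check.

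**Inputs.** From the documents: three conditions, three stimulation visits, three groups named by first condition, 124 complete data sets from up to 150 enrolled. Assumed: an additive practice effect, linear in visit, of 0.2 to 0.4 outcome SD per visit.

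**Step 1: possible order sets.** There are 3! = 6 orders. Each first condition leaves two ways to arrange the other two, so fixing one order per group gives 2 × 2 × 2 = 8 sets. Write S, A, C for sham, anodal, cathodal, and number the stimulation visits 1 to 3. With equal groups, the bias in an unadjusted contrast is (difference in mean visit) × (change per visit).

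| Orders | Mean visit S, A, C | A − S bias | C − S bias | Relative variance of A − S with visit term |
|---|---|---|---|---|
| SAC, ACS, CSA | 2.00, 2.00, 2.00 | 0 | 0 | 2.0 |
| SCA, ASC, CAS | 2.00, 2.00, 2.00 | 0 | 0 | 2.0 |
| SAC, ASC, CSA | 1.67, 2.00, 2.33 | +1/3 | +2/3 | 2.4 |
| SAC, ASC, CAS | 2.00, 1.67, 2.33 | −1/3 | +1/3 | 2.4 |
| SAC, ACS, CAS | 2.33, 1.67, 2.00 | −2/3 | −1/3 | 3.6 |
| SCA, ASC, CSA | 1.67, 2.33, 2.00 | +2/3 | +1/3 | 3.6 |
| SCA, ACS, CSA | 2.00, 2.33, 1.67 | +1/3 | −1/3 | 2.4 |
| SCA, ACS, CAS | 2.33, 2.00, 1.67 | −1/3 | −2/3 | 2.4 |

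Bias is in units of the per-visit change. Relative variance is N × variance / residual variance. For example, in SAC, ASC, CSA, sham falls at visits 1, 2, 2 (mean 5/3) and cathodal at 3, 3, 1 (mean 7/3), a difference of 2/3.

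**Step 2: size.** The smallest non-zero bias is 1/3 × 0.2 = 0.07 SD and the largest is 2/3 × 0.4 = 0.27 SD. A visit term removes this bias in all six unbalanced sets, at the variance shown. Six equal orders have no linear visit bias and a relative variance of 2.0.

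**Step 3: dropout from a Latin square.** For SAC, ACS, CSA with n1, n2, n3 completers and N in all, the A − S difference in mean visit is (n1 − 2·n2 + n3)/N = 1 − 3·n2/N. Equal numbers give 0. Suppose 150 are enrolled at 50 per group and all 150 − 124 = 26 losses fall in the second group. Then n2 = 24, and the difference is 1 − 72/124 = 0.42 of the per-visit change. That is the extreme case. An assumed split of 46, 38, 40 gives 1 − 114/124 = 0.08.

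**Step 4: balanced orders, no visit term.** A linear effect of δ per visit adds 2δ² per participant to the within-participant sum of squares. Spread over 2(N − 1) error degrees of freedom, it raises the error variance by δ² × N/(N − 1), about δ². With residual variance 1 this is 0.2² = 4% to 0.4² = 16%. If δ is in outcome SDs and sessions are positively correlated, the residual variance is smaller and the inflation larger. Fitting visit takes the error degrees of freedom from 2 × 123 = 246 to 244.

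**Step 5: carryover, as a side check.** In the two Latin squares each condition only ever follows one other condition. Fitting first-order carryover would raise the relative variance of A − S from 2.0 to 10.0, against 2.0 to 2.5 with six equal orders.

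**The case against.** Several stronger readings are tempting, and the documents do not support them.

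- A reader might infer that the two sections contradict each other, because a random order implies all six. It does not: random assignment to one of three fixed orders is also a random order. The allocation sentence may even be shorthand that labels groups by first condition. The sections are ambiguous together and need reconciling.
- A reader might infer that three orders bias the contrasts by themselves. They do not. If the groups rotate as a Latin square, any additive visit effect cancels from the condition means. Two sets in eight is a count, not a probability, and nothing says that an unbalanced set was used.
- A reader might infer that each condition is confounded with residual stimulation from the session before. The documents set a washout of at least one week against effects thought to last hours. General learning is a visit effect and acts as carryover only if it depends on the preceding condition, for which there is no evidence here. The fivefold variance increase arises only if a carryover term is fitted, and neither the plan nor the fix below includes one.

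The practice effect is also assumed, and nothing in the documents supports its size for the MEG outcomes. A stated Latin square with a visit term would answer the practice concern as well as six orders would.

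All of this stands. It does not supply the missing order list, a statement of balance, or a visit term.

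**Conclusion.** The point holds in a limited form. Read literally, the allocation uses three of six orders; their balance is not stated, and no planned analysis adjusts for visit. If the set is not a Latin square, unadjusted condition contrasts carry 1/3 to 2/3 of the per-visit practice change, or 0.07 to 0.27 SD under the stated assumption. For scale, that is 0.07/0.96 = 7% to 0.27/0.96 = 28% of the preliminary d, if the SDs are comparable. If it is a Latin square with even completion, there is no additive visit bias, and the loss is an error variance inflated by roughly 4% to 16%. Uneven dropout lies between.

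This shows exposure, not proven bias. It rests on an additive, linear practice effect whose size the documents do not give. Carryover is a secondary concern. The visit term is worth having on every reading: it removes additive visit bias from unbalanced orders and takes visit variance out of the error when they are balanced.

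**What to change.** 1. Add visit number (2, 3, 4) as a within-participant factor, alongside condition, in the behavioural ANOVAs, the SPM models for alpha and gamma, and the cluster ANOVAs.
2. Reconcile the allocation sentence in the Study Protocol section with Sample Size Considerations by listing the orders and the allocation to each. Preferably use all six (SAC, SCA, ASC, ACS, CSA, CAS) in equal numbers, in permuted blocks of six: 124/6, or about 20 to 21 complete data sets per order. A stated Latin square is the minimum, at 124/3, or about 41 per order.
3. If enrolment is complete, report the orders used and the number of completers in each, and fit the visit term.

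The visit factor costs 2 error degrees of freedom. The order change costs a new randomization list and a sentence of protocol text. Neither needs extra participants, visits or procedures.

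### Does a power statement for 34 per parallel group leave the 124-participant crossover and its Bonferroni-corrected brain maps without adequate power?

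*Combined protocol and SAP*

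**What the plan says.** Sample Size Considerations takes a Cohen's d of 0.96, the average over stimulation group differences. The investigators "computed Cohen's d using data from a perceptual processing task where participants were assigned to a single stimulation type", so the pilot was a between-subjects study. The text continues: "This suggests that 34 participants per group (anode, cathode, sham) would be adequate to detect differences at 0.01 alpha with 0.90 power". It then says that this study is a crossover, that a within-subject effect might be larger but need not be, and that "investigators should be powered to examine sex differences in the impact of tDCS on spontaneous and oscillatory neural activity in future work". The conclusion is: "Thus, the aim is 124 complete data sets", with up to 150 enrolled to allow for attrition and for MEG failure in 3-5%.

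Primary Statistical Analyses plans one ANOVA per behavioural measure. For MEG it plans whole-brain F-tests on "neural response amplitude values in each of thousands of voxels", then ANOVAs per significant cluster, with alpha and gamma handled separately. It ends by saying that "multiple comparisons correction will use the Bonferroni method". It does not say whether the family is voxels, clusters, pairwise comparisons or bands. The Study Protocol section defines the outcomes as changes "induced by the different types of stimulation relative to sham".

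**The concern.** Three things do not line up.

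- **Test and threshold.** The only power figure belongs to a two-group parallel comparison at 0.01. The trial has no parallel groups, and if Bonferroni runs over voxels, the threshold at each voxel is far below 0.01.
- **Planning effect.** An average over group differences may include the anode-cathode gap, whereas the outcomes are defined against sham. If that gap is the largest of the three, 0.96 overstates the effect that matters.
- **The number 124.** It is none of 2 × 34 = 68, 3 × 34 = 102 or 6 × 34 = 204, and no calculation for sex differences is given.

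If these gaps hid a real shortfall, the trial could produce empty brain maps that readers would take as evidence of no effect, and later work on sex differences would start from a false assurance.

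**Working it through.** **1. The plan's own figure.** Inputs from Sample Size Considerations: d = 0.96, alpha 0.01, n = 34 per group. The test and sidedness are not stated. For a two-sided two-sample t-test, power = P(T > t_crit), where T is noncentral t with 2n − 2 = 66 degrees of freedom and noncentrality d√(n/2) = 0.96 × √17 = 3.96, and t_crit = 2.65. The result is 0.9001; n = 33 gives 0.889. So 34 is the smallest n that reaches 0.90, and the stated figure is correct for that test.

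**2. The same 34 per group at stricter thresholds.** Only three pairwise comparisons corrected (0.01/3): power 0.81. Voxelwise Bonferroni at familywise 0.05: 0.37 (1,000 voxels), 0.23 (5,000), 0.18 (10,000). The voxel counts are assumptions, since the plan says only thousands. These figures look alarming, but they describe a parallel trial with 34 per arm, which is not what is planned.

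**3. The planned trial.** With N = 124 and a paired comparison of two conditions, the standardized within-person difference is dz = d/√(2(1 − ρ)), where ρ is the within-person correlation (not given in the plan). The noncentrality is dz√N with N − 1 = 123 degrees of freedom. The least favourable value considered is ρ = 0: dz = 0.96/√2 = 0.679 and noncentrality 0.679 × √124 = 7.56.

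| Threshold | Power, N = 124, d = 0.96, ρ = 0 |
|---|---|
| 0.01 | > 0.999 |
| 0.05/1,000 | 0.999 |
| 0.05/5,000 | 0.998 |
| 0.05/10,000 | 0.996 |
| 0.01/10,000 | 0.989 |

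A positive ρ raises every entry.

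**4. Comparison with sham.** Suppose that 0.96 averages all three pairs and that anodal and cathodal effects are equal and opposite, each x from sham. Then (x + x + 2x)/3 = 0.96, so x = 0.72. The plan states neither condition. With N = 124 and ρ = 0, power for d = 0.72 is 0.999 at alpha 0.01, and 0.92, 0.85 and 0.81 at 0.05 divided by 1,000, 5,000 and 10,000 voxels. These are for a single paired contrast; the planned F-test also draws on the anode-cathode difference of 1.44.

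**5. What 124 can detect at 90% power.** 0.35 SD of the within-person difference at alpha 0.01, and 0.50 to 0.55 SD at familywise 0.05 over 1,000 to 10,000 voxels.

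**6. Sex differences.** With an assumed 62 per sex (124/2), the detectable difference between the sexes in the within-person contrast is 0.70 SD at alpha 0.01, and 0.99 to 1.10 SD over 1,000 to 10,000 voxels. If the sexes differ by half of 0.96, power at 0.01 is 0.24, 0.52 or 0.80 for ρ = 0, 0.5 or 0.7. The result depends mainly on inputs that the plan does not supply.

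**The case for a change.** The strongest case for changing the text is that 124 is ample only if the pilot effect holds. At d = 0.5 and 0.05/5,000, power with 124 is 0.26 for ρ = 0 and 0.82 for ρ = 0.5. A reader faced with an empty map would want the detectable effect stated at the threshold actually used. Sex is also an express reason for the larger target, so a supporting calculation would be natural. Admitting that the pilot was between-subjects does not supply a crossover calculation.

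These points stand as comments on reporting. They do not show that the trial falls short of anything it claims. A smaller true effect threatens any trial planned from pilot data, and the plan already guards against it: it declines to rely on a gain from the within-subject design and sets a target more than three times the 34 it calculated (124/34 = 3.6). The voxelwise reading of Bonferroni is reasonable but not explicit. The make-up of 0.96 is not described either; it may be behavioural, in which case voxel correction does not bear on it. For sex differences no power is stated, so there is no figure to correct.

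**Conclusion.** No change to the plan follows. The 34-per-group figure is arithmetically correct for the test it describes, and the plan itself says that its effect size comes from a different design. The trial to be run has 124 crossover data sets. On the pilot effect, its power for a paired contrast is at least 0.989 under every threshold in the table, with ρ = 0. On the less favourable versus-sham reading (0.72), it is 0.999 at alpha 0.01 and 0.81 to 0.92 under voxelwise correction with ρ = 0.

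What remains is missing detail: no derivation of 124, no power at the corrected threshold, and no calculation behind the remark on future sex analyses. Supplying it would leave the sample size, the design and the analysis as they are. The conclusion rests on assumed voxel counts, on d = 0.96 as reported, and on paired t-tests standing in for the planned F-test. It does not extend to sex differences, for which the plan claims no power.

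### The ANOVAs compare stimulation conditions with no visit term, and balance of the conditions over Visits 2-4 is not shown

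*Combined protocol and SAP*

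**What the plan says.** Under Study Protocol, participants have four visits at least a week apart. Visits 2 to 4 each deliver one stimulation condition, followed by an MEG session with the perceptual task. Before Visit 2 each participant is "randomized to the sham, anode, or cathode-first group, which will determine the stimulation montage for each of their subsequent visits". Sample Size Considerations adds that "each participant will complete all three stimulation conditions in a random order". Neither place gives the order of the second and third conditions, the number of sequences or the allocation ratio.

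Primary Statistical Analyses describes three sets of comparisons:

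- **Behaviour:** "investigators will compute mean accuracy and reaction time for each stimulation condition, which will be the outcome metrics"; these "can be assessed using an ANOVA per measure with follow-up post-hoc testing to identify the specific direction of any significant effects".
- **Voxelwise MEG:** "The resulting statistical F-maps of neural oscillatory activity will reveal brain areas with significant differences by stimulation condition".
- **Spontaneous activity at the cluster peaks:** "For these analyses, separate ANOVAs will be computed for each cluster", again by stimulation condition.

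No visit, period or sequence term appears in any of them. The section also does not say that the ANOVAs are repeated-measures. The one-week interval is justified by how long tDCS effects last, so it deals with carryover and not with practice, habituation or fatigue.

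**The concern.** In a three-period cross-over, a change over periods is separated from the treatment comparison either by balance of the sequences or by a period term in the model. Here the model has no such term and the sequences are not stated. If an outcome does change over visits, there are three possible consequences:

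1. **Orders balanced over visits.** Contrasts are unbiased, but the visit change goes into the error term, so tests are conservative and lose power.
2. **Unrestricted random orders.** Contrasts are less precise; false-positive rates stay correct.
3. **Orders unbalanced, by design or by dropout.** The contrasts with sham are biased.

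The outcomes are defined relative to sham, so in the third case a practice or fatigue trend would be read as a stimulation effect, or would hide one. Dropout matters because the plan expects that "enrollment up to 150 participants to reach this number may be needed, as the multiple visits could lead to larger attrition".

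**Working it through.** **The plan's own figure.** For d = 0.96, two-sided alpha 0.01 and two independent groups, the exact t-test power is 0.889 at 33 per group and 0.900 at 34. The stated 34 is reproduced. It is a between-group calculation ("the preliminary data used to calculate effect sizes followed a between-subjects design") and contains no visit effect.

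**Inputs.** From the documents: 124 complete data sets, up to 150 enrolled, three first-condition groups. Assumed: participant is in the model (the reading most favourable to the plan), and the change per visit, in within-subject SD. The SE of a contrast is √(2/124) = 0.127.

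**Step 1: balance.** Each first-condition group can take one of two fixed sequences, giving 2 × 2 × 2 = 8 schemes. Write S, A, C for sham, anode, cathode. In S-A-C / A-S-C / C-S-A the mean visit positions are:

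- S: (1+2+2)/3 = 1.667
- A: (2+1+3)/3 = 2.000
- C: (3+3+1)/3 = 2.333

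So C−S = 0.667 and A−S = 0.333. Over all eight schemes, two are Latin squares with no difference in position. In four, one sham contrast is shifted by two-thirds of a linear per-visit change and the other by one-third. In two, both are shifted by one-third. These fractions need no assumed effect.

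**Step 2: false positives when unbalanced, no visit term.** In the example, with 0.3 SD per visit:

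- Cathode minus sham shifts by 0.667 × 0.3 = 0.20 SD.
- The visit sum of squares is 124 × 0.18 = 22.32. The condition term absorbs 124 × 0.02 = 2.48. Error inflation is 1 + 19.84/246 = 1.08.
- Rejection at 5% ≈ P(Z > 1.970 × √1.08 − 0.20/0.127) = P(Z > 0.47) ≈ 0.32.

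| Change per visit (SD) | Two-thirds shift (SD) | Rate at nominal 5% | One-third shift: rate at 5% |
|---|---|---|---|
| 0.1 | 0.07 | 8% | 6% |
| 0.2 | 0.13 | 17% | 7-8% |
| 0.3 | 0.20 | 31-33% | 10-11% |

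The ranges reflect groups of 42/41/41. At nominal 1% and 0.3 per visit the rates are 12.4-13.6% and 2.6-3.0%. Simulation of the example (10,000 runs, no true effect, 0.3 per visit) rejects 34.2% at 5% without the visit term and 5.1% with it.

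**Step 3: dropout from a Latin square.** As a bound, let 50/50/50 lose all 26 from one group, leaving 24/50/50. The largest sham-contrast shift is |3 × 24 − 124|/124 = 0.419 of a per-visit change. At 0.3 per visit that is 0.126 SD, with a 5% test rejecting about 14% of the time.

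**Step 4: power when balanced.** Inflation = 1 + (sum of squared visit deviations / 2) × 124/123. Power for one contrast of 0.4 SD at alpha 0.01 = P(Z > 2.596 × √inflation − 0.4/0.127).

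| Assumed visit means (SD) | Inflation | Power without term | Power with term |
|---|---|---|---|
| 0.3 per visit, linear | 1.091 | 0.67 | 0.71 |
| 0 / −0.5 / −0.75 | 1.147 | 0.64 | 0.71 |
| 0 / −1 / −1.5 | 1.588 | 0.45 | 0.71 |

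At 0.96 SD, power is essentially 1.00 in every row, with or without the term.

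**Step 5: unrestricted random orders.** In the same three cases (4,000 simulated runs each) the SD of the contrast rises from 0.127 to 0.131, 0.136 and 0.161. False positives at 5% are 4-5%.

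**Scale.** The pilot d is in between-subject SD. In within-subject SD it is 0.96/√(1 − r), which is 0.96, 1.15, 1.36 or 1.75 at assumed within-person correlations r of 0, 0.3, 0.5 or 0.7. Conversely, 0.4 within-subject SD is 0.40, 0.33, 0.28 or 0.22 on the pilot scale. No voxelwise power is claimed.

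**The case against.** The serious harm needs two things the documents do not show: a real change over Visits 2 to 4, and sequences that are unbalanced. Random order may well mean all six orders with equal probability, in which case the contrasts are unbiased and error rates hold. Six of eight is a count of possible schemes, not a probability; a simple rotation is a common choice and is balanced. The worked sequence set is an illustration and does not appear in the plan. The dropout bound is extreme: some of the loss is put down to MEG technical trouble in 3-5% of participants, which has no reason to follow sequence. At the planned effect size power is ample whatever is done. Finally, the analysis section is a summary that does not even name participant, so silence about visit does not exclude it.

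Most of this stands as a limit on size. It does not remove the point. Ample power gives no protection against bias, balance is undocumented, the wash-out argument covers carryover only, and as written every comparison is by condition alone. A model with visit is better than that whenever a visit change exists, whichever sequences were used.

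**Conclusion.** The concern holds, as a change that should be made and not as a demonstrated error in results. No visit term is planned in any of the three sets of analyses, and balance over visits cannot be established from the documents. The shifts of one-third and two-thirds of a per-visit change follow from the enumeration alone, given one fixed sequence per group. The false-positive and power figures also rest on assumed visit changes, 124 completers and participant being in the model. With unbalanced sequences and a change of 0.1 to 0.3 SD per visit, a contrast with the larger shift has a 5% test rejecting about 8% to 33% of the time under no effect. With balanced or random orders the loss is confined to power for effects well below the planned one. If visit change is negligible, nothing is lost by the present model.

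**What to change.** Analyse each behavioural, voxelwise and cluster measure with a within-participant model: participant as a blocking or random factor, with stimulation condition and visit number as fixed factors (visit regressors in the SPM12 design). Report visit-adjusted contrasts of anodal and cathodal stimulation against sham. State the sequences used and the number of completers in each.

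The cost is SAP wording and 2 of about 246 error degrees of freedom; visit number is already known. If the sequences prove unbalanced, the adjusted contrasts are valid but less precise. The SE rises from 0.127 to 0.139 or 0.170, giving power of 0.61 or 0.40 for a 0.4 SD effect at alpha 0.01, and above 0.998 at 0.96 SD.

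### Does testing reaction time and accuracy in separate ANOVAs, with no rule for reading them together, let a speed-accuracy trade-off pass as a benefit?

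*Combined protocol and SAP*

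**What the plan says.** All the relevant text is in the combined protocol and SAP.

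- **Definitions (Primary Statistical Analyses).** Accuracy is "the percentage of trials where the participant responded correctly". Reaction time "will be the average of all correct trials during the perceptual processing task", a task of 240 trials.
- **Outcome metrics (same section).** After the per-person values, "investigators will compute mean accuracy and reaction time for each stimulation condition, which will be the outcome metrics". This step does not depend on any test result.
- **Favourable direction (same section).** "Faster reaction times and higher accuracy reflect more favorable outcomes following the particular type of stimulation relative to sham".
- **Test (same sentence).** These outcomes "can be assessed using an ANOVA per measure with follow-up post-hoc testing to identify the specific direction of any significant effects".
- **Status of the two measures (Study Protocol).** Reaction time and accuracy are listed side by side as behavioural outcomes, compared with sham. Neither ranks above the other.

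The documents give no composite measure, no multivariate test, no order between the two measures, no interval for the accuracy difference and no rule for results that point in opposite directions.

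**The concern.** Reaction time and accuracy come from the same trials, and one change in how cautiously a person responds moves both. Averaging reaction time over correct trials does not remove that link. The case at issue is a mixed one: the reaction-time ANOVA is significant in the faster direction and the accuracy ANOVA is not significant. Post-hoc testing of direction is then triggered for reaction time but not for accuracy. A non-significant accuracy result does not show that accuracy was preserved, so a modest shift to quicker, less careful responding might be written up as an improvement due to stimulation. At stake is the behavioural interpretation of the trial: a change in strategy could be mistaken for better visual processing.

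**Working it through.** **1. The plan's own figure.** Sample Size Considerations gives 34 per group for d = 0.96, alpha 0.01 and power 0.90. The two-sided normal approximation is n = 2(2.576 + 1.282)²/0.96² = 29.77/0.9216 = 32.3, so 33. The exact two-sided t test gives 34 (power 0.900). The figure reproduces. It does not bear on this question, because d is one average between-subject value, not split by measure.

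**2. What 124 complete data sets can detect.** In a paired comparison, the standardised difference (dz) detectable with 80% power is 0.254 at alpha 0.05 and 0.294 at 0.05/3. Smaller accuracy losses will often miss significance. Suppose a true reaction-time gain of dz 0.40, alpha 0.05 and Bonferroni follow-up over three pairs (all assumed). The chance that reaction time is declared faster while the accuracy loss is not declared is then:

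| True accuracy loss (dz) | Chance |
|---|---|
| 0.10 | about 88% |
| 0.20 | 57-59% |
| 0.30 | 17-18% |
| 0.40 | 2-3% |

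At alpha 0.01 these become 89-91%, 71-73%, 32-33% and 6-7%. The exposure is to small trade-offs.

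**3. The same in milliseconds and percentage points.** Only N = 124 and 240 trials come from the documents; all else is assumed. In a simple diffusion model with drift v and boundary a, accuracy = 1/(1 + exp(-av)) and mean decision time = (a/2v) tanh(av/2). Cutting a by 5% with v unchanged gives:

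- v = 2, a = 1.5: accuracy 95.26% to 94.53% (0.73 points lower), decision time 22 ms faster.
- v = 2.5, a = 1.4: 97.07% to 96.53% (0.54 points), 16 ms faster.
- v = 2, a = 1.3: 93.09% to 92.20% (0.88 points), 19.5 ms faster.

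The mixed result is defined as reaction-time ANOVA p < 0.05 with Bonferroni follow-up faster than sham, and accuracy ANOVA p ≥ 0.05. It was simulated with 4,000 runs per setting and one active condition shifted. The interval half-width is t(0.975, 123) × SD/√124 = 1.979 × SD/11.14 = 0.178 × SD. Ranges are over the three (v, a) settings.

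| SD of accuracy difference (points) | Mixed result, reaction-time SD 60 ms | Mixed result, reaction-time SD 100 ms | Of mixed results at 60 ms, mean accuracy below sham | 95% CI half-width (points) |
|---|---|---|---|---|
| 3 | 6-34% | 2-13% | 96-99% | 0.5 |
| 4 | 25-48% | 12-24% | 92-99% | 0.7 |
| 5 | 43-61% | 17-35% | 86-95% | 0.9 |
| 8 | 63-80% | 23-43% | 76-86% | 1.4 |

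With binomial noise only (SD 1.6-2.4 points) the mixed result has a chance of 1-2% at 60 ms. With a 10% cut at 60 ms it is 0% at SD 3, 0-7% at SD 4, 1-23% at SD 5 and 23-62% at SD 8. With a 3% cut at 60 ms it is 20-47% over SDs of 3 to 8.

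**4. Would the condition means show the loss?** The chance that mean accuracy falls below sham is about Φ(loss × √124/SD), before conditioning on the test results. For a loss of 0.54 points this is Φ(0.54 × 11.14/3) = Φ(2.0) = 98% at SD 3, and Φ(0.54 × 11.14/8) = Φ(0.75) = 77% at SD 8. These agree with the fourth column.

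**5. Reading the text.** Condition means for both measures are computed unconditionally. Only the post-hoc test of direction depends on significance. An estimate of the accuracy difference from sham, with its sign, is therefore always available by subtraction.

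**The case for a change.** The strongest case for a change is that condition means alone are not enough. Two means without an interval for their within-person difference cannot show whether a loss of 0.5 to 0.9 points is excluded. The favourable-direction sentence names both measures but is not written as a rule requiring both, and the same sentence tests them separately. The remedy would be cheap: two or three sentences and one interval per contrast.

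Most of this is true. The plan prespecifies neither the interval nor the joint reading, and a non-significant accuracy test is not evidence of preserved accuracy. But the argument establishes a reporting preference rather than a fault. The addition would alter no test, sample size or data collection. The interval comes from data the plan already collects, and anyone reporting both outcomes can add it. Nor do the documents suggest that stimulation alters response caution. The high probabilities need an accuracy-difference SD of up to 8 points when only 3-7% of responses are assumed to be errors, together with a reaction-time SD near 60 ms; the documents support neither.

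**Conclusion.** The observation about the text is right, but no change is needed. This is missing detail that analysts fill sensibly. Following the plan as written gives a test for each measure and both sets of condition means side by side, with the favourable direction of each stated. The plan does not say that faster responding alone counts as a benefit, and an accuracy loss of dz 0.40 would go undeclared in only 2-3% of trials at alpha 0.05.

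The residual exposure is to small trade-offs, and its size is not determined by the documents. For an assumed 5% cut in caution, the chance of the mixed result runs from 1-2% to 63-80% at a reaction-time SD of 60 ms. At 100 ms it runs from 2-13% to 23-43% over accuracy SDs of 3 to 8 points. These figures rest on the assumed diffusion settings, on the assumed SDs of both differences, on alpha 0.05 with Bonferroni follow-up over three pairs, and on stimulation shifting caution at all. Even in the mixed cases at 60 ms, the accuracy mean lies below sham 76-99% of the time over accuracy SDs of 3 to 8, so a careful reader would see the pattern.
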